7.6.5 Other Efficacy Analysis

Descriptive statistics for the other efficacy endpoints will be presented by treatment group and by study visit/week where appropriate. Data from all study visits, scheduled and unscheduled, will be listed.

7.6.5.1 Change from Baseline to Week 6 in the NPSI

The NPSI, a 12-item questionnaire, assesses the different components of neuropathic pain syndromes (ie, spontaneous ongoing and paroxysmal pain, evoked pain, paresthesia/dysesthesia). 10-items related to different pain descriptors (eg, burning, squeezing, electric-shock, stabbing, tingling) allows assessment of the different dimensions of neuropathic pain and 2 items on frequency and duration of pain.

The total intensity score and the 5 subscores (burning spontaneous pain, pressing spontaneous pain, paroxysmal pain, evoked pain, and paresthesia/dysesthesia) will be calculated as:

- Total intensity score: $Q1+Q2+Q3+Q5+Q6+Q8+Q9+Q10+Q11+Q12$
- (Superficial spontaneous) Burning pain: $Q1$
- (Deep spontaneous) Pressing pain: $(Q2+Q3)/2$
- Paroxysmal pain: $(Q5+Q6)/2$
- Evoked pain: $(Q8+Q9+Q10)/3$
- Paresthesia/dysesthesia: $(Q11+Q12)/2$

Baseline will be the data collected on Day 1 at Visit 3. The change from Baseline to Week 6 in total intensity score and the 5 subscores will be summarized using standard descriptive statistics and the treatment effect will be evaluated using an ANCOVA model fitted for the fixed effects of treatment, the randomization stratum of Baseline pain severity (moderate, severe), and the continuous fixed covariate of Baseline score. The ANCOVA analysis will be performed at Week 6 only.

The adjusted mean change from Baseline to Week 6 for each treatment group and the 95% CIs will be estimated in the framework of this model, as well as the between-group differences (comparing each LX9211 treatment group to placebo) and the 95% CIs for the difference.

Summarization of the inferential statistics will include the LS means, SE of the estimates, p-values, and 2-sided 95% CIs. These statistics will be provided for the

CONFIDENTIAL

Document Date: 07JUN2022

Page 34 of 55

ST-AD-008 version 05

within treatment group changes from Baseline and for the comparison of LX9211 versus placebo for the change from Baseline scores. Tabulation of the inferential results (CIs and p-values) will include the observed model findings.

7.6.5.2 Change in Question 5 of the BPI-DPN from Baseline to each post-Baseline visit

Baseline will be the data collected on Day 1 at Visit 3. For this endpoint, we will use the Question 5 of the BPI-DPN, collected at clinic visits and visit windows defined in [section 6.1.2](#). The values collected for each post-Baseline visit and the change from Baseline at post-Baseline visits will be summarized by visit and treatment group using standard descriptive statistics. The treatment effect will be evaluated using a similar MMRM method as specified for the primary efficacy analysis of change from Baseline to Week 6.

The change from Baseline values at post-Baseline visits will be calculated as the absolute difference between Baseline value and post-Baseline values, ie,

$$\text{Change from Baseline} = \text{post-Baseline value} - \text{Baseline value}$$

7.6.5.3 Proportion of patients with $\geq 30\%$ reduction from Baseline in ADPS, based on Question 5 of the BPI-DPN by week

Baseline and weekly ADPS scores will be based on the mean values as described in the primary efficacy analysis. Missing ADPS scores derivations at any week will be imputed as non-response. The frequency and percentages of patients with $\geq 30\%$ reduction in pain intensity from Baseline, based on Question 5 of BPI-DPN collected each evening on the e-diary, will be presented by Week and treatment group.

7.6.5.4 Proportion of patients with $\geq 50\%$ reduction from Baseline in ADPS, based on Question 5 of the BPI-DPN by week

Baseline and weekly ADPS scores will be based on the mean values as described in the primary efficacy analysis. Missing ADPS scores derivations at any week will be imputed as non-response. The frequency and percentages of patients with $\geq 50\%$ reduction in pain intensity from Baseline, based on Question 5 of BPI-DPN collected each evening on the e-diary, will be presented by Week and treatment group.

7.6.5.5 Cumulative distribution function of percent change in ADPS based on Question 5 of the BPI-DPN from Baseline to Week 6 comparing the LX9211 treatment group to placebo

Baseline and Week 6 ADPS scores will be based on the same mean values as derived for the primary endpoint. A descriptive plot of the cumulative distribution function of percent change from Baseline to Week 6 in ADPS based on Question 5 of

the BPI-DPN collected each evening on the e-diary will be presented by treatment group.

% change from Baseline to Week 6 = $100 * (\text{Week 6 value} - \text{Baseline value}) / \text{Baseline value}$.

7.6.5.6 Cumulative distribution function of percent change in ADPS based on Question 5 of the BPI-DPN from Week 6 to Week 11 comparing the LX9211 treatment group to placebo

Week 6 and Week 11 ADPS scores will be based on the mean weekly values as described in the primary efficacy analysis. A descriptive plot of the cumulative distribution function of percent change from Week 6 to Week 11 in ADPS based on Question 5 of the BPI-DPN collected each evening on the e-diary will be presented by treatment group. Where percent change from Week 6 to Week 11 will be defined as:

% change from Week 6 to Week 11 = $100 * (\text{Week 11 value} - \text{Week 6 value}) / \text{Week 6 value}$.

7.6.5.7 Change in Question 8 of the BPI-DPN from Baseline to each post-Baseline visit

Baseline will be the data collected on Day 1 at Visit 3. For this endpoint, we will use the Question 8 of the BPI-DPN, collected at clinic visits and visit windows defined in [section 6.1.2](#). The values collected for each post-Baseline visit and the change from Baseline at post-Baseline visits will be summarized by visit and treatment group using standard descriptive statistics. The treatment effect will be evaluated using a similar MMRM method as specified for the primary efficacy analysis of change from Baseline to Week 6.

The change from Baseline values at post-Baseline visits will be calculated as the absolute difference between Baseline value and post-Baseline values, ie,

Change from Baseline = post-Baseline value – Baseline value

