10.3.3 Other Efficacy Endpoints

Other efficacy endpoints are:

- 1. Change from Baseline to Week 6 in the Neuropathic Pain Symptom Inventory (NPSI)
- 2. Change from Baseline to each week in ADPS, based on Question 5 of the BPI-DPN
- 3. Proportion of patients with ≥30% reduction from Baseline in ADPS, based on Question 5 of the BPI-DPN by week
- 4. Proportion of patients with ≥50% reduction from Baseline in ADPS, based on Question 5 of the BPI-DPN by week
- 5. Cumulative distribution function of percent change in ADPS based on Question 5 of the BPI-DPN from Baseline to Week 6 comparing each LX9211 treatment group to placebo
- 6. Cumulative distribution function of percent change in ADPS based on Question 5 of the BPI-DPN from Week 6 to Week 11 comparing each LX9211 treatment group to placebo

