3.1 Primary Efficacy Endpoint

The primary efficacy endpoint is the change from Baseline (Week 2 of the Run-in Period) to Week 6 in ADPS, based on Question 5 of the Brief Pain Inventory - DPN (BPI-DPN), the 11-point scale (0 [no pain] to 10 [pain as bad as you can imagine]).

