3.3 Other Efficacy Endpoints

The other efficacy endpoints are to be assessed in each LX9211 dose group versus placebo comparison for each of the following variables listed below:

- Change from Baseline to Week 6 in the NPSI
- Change from Baseline to each week in ADPS, based on Question 5 of the BPI-DPN
- Proportion of patients with $\geq 30\%$ reduction from Baseline, based on Question 5 of the BPI-DPN by week
- Proportion of patients with $\geq 50\%$ reduction from Baseline, based on Question 5 of the BPI-DPN by week

- Cumulative percentage of percent change in ADPS based on Question 5 of the BPI-DPN from Baseline to Week 6 comparing each LX9211 treatment group to placebo
- Cumulative percentage of percent change in ADPS based on Question 5 of the BPI-DPN from Week 6 to Week 11 comparing each LX9211 treatment group to placebo

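### The Week 6 to Week 11 change in pain is plotted as a percentage of the Week 6 score, a denominator that treatment is meant to lower and that can be 0

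*SAP*

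**What the plan says.** Among the measures that Protocol 10.3.3 places below the secondary endpoints is this one: "Cumulative distribution function of percent change in ADPS based on Question 5 of the BPI-DPN from Week 6 to Week 11". Each dose group is to be set against placebo. SAP 3.3 carries it over with a small change of wording, which begins "Cumulative percentage of percent change in ADPS based on Question 5 of the BPI-DPN from Week 6 to Week 11 comparing each". Neither place states the denominator.

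SAP 7.6.5.6 does. "Week 6 and Week 11 ADPS scores will be based on the mean weekly values as described in the primary efficacy analysis", that is, means of the daily diary scores. The formula introduced by "Where percent change from Week 6 to Week 11 will be defined as" is 100 x (Week 11 value - Week 6 value)/Week 6 value. What is shown is the "cumulative distribution function of percent change from Week 6 to Week 11 in ADPS", as a descriptive plot by treatment group with no test, and the heading of the section gives the purpose: "from Week 6 to Week 11 comparing the LX9211 treatment group to placebo".

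The companion plot in SAP 7.6.5.5, for Baseline to Week 6, divides by Baseline instead. The pain scale starts at 0 (SAP 3.1). A weekly mean needs at least 4 diary days (SAP 6.1.1), so it is 0 when every recorded day is 0. SAP 6.1.1, 6.2 and 7.6.5.6 give no rule for a Week 6 mean of 0.

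**The concern.** After Week 6 all arms take single-blind placebo, so this plot describes how far pain returns once LX9211 is withdrawn. Its denominator is measured after randomization and on treatment, and the drug is meant to reduce it. A between-arm difference in the plotted percentages therefore mixes two things: how much pain changed after Week 6, and how low it was at Week 6.

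If the drug works, the same rise in points is divided by a smaller number on LX9211. A reader could take the resulting gap for a withdrawal or rebound effect. Patients with no pain at Week 6 drop off the plot, and more of them would be expected on the effective arm. Patients close to 0 produce very large percentages: a move from 0.5 to 2 is 100 x 1.5/0.5 = +300%.

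What is at stake is how a descriptive figure is read. Type I error, power and the primary comparison are not involved.

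**Working it through.** **Inputs from the documents.** A 1-unit treatment difference and an SD of 2 (Protocol 10.1, SAP 2.3); a scale from 0 to 10 (SAP 3.1); randomization strata of 5-7 and 8-9 (SAP 7.2), which keep Baseline well above 0. The plan gives no figure for this endpoint. Its sample size, the source of the 1-unit difference, does reproduce: 75 completers per arm give 80.7% power by normal approximation at two-sided 0.0282 (2 x 0.0141 from SAP 7.8). Then 75/(1 - 0.20) = 93.75, rounded up to 94, and 3 x 94 = 282.

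**Step 1: arithmetic of an equal rebound.** Both arms rise by 1 point, with Week 6 means 1 point apart. Percent change = 100 x 1/Week 6.

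| Week 6, placebo / LX9211 | Placebo | LX9211 | Ratio |
|---|---|---|---|
| 5.5 / 4.5 | 18.2% | 22.2% | 1.22 |
| 5 / 4 | 20% | 25% | 1.25 |
| 4 / 3 | 25% | 33.3% | 1.33 |
| 3 / 2 | 33.3% | 50% | 1.50 |

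**Step 2: how far this moves the curves.** The simulation uses 400,000 patients per arm. Assumptions, none taken from the documents: Week 6 means of 4 (LX9211) and 5 (placebo), SD 2, limited to 0-10 on a 1/7 grid; Baseline 6.5. The plan's SD of 2 is for the change score and is only borrowed here for the Week 6 score. Three patterns after Week 6, identical in both arms:

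| Pattern | Measure | LX9211 | Placebo |
|---|---|---|---|
| Additive, mean +1 point, SD 1.2 | at least 30% worse, SAP scale | 42.8% | 34.2% |
| | at least 50% worse, SAP scale | 24.4% | 16.1% |
| | rise of at least 30% of Baseline | 21.0% | 20.1% |
| Additive, mean 0, SD 1.2 | at least 30% worse, SAP scale | 17.5% | 12.8% |
| | at least 30% better, SAP scale | 17.5% | 12.9% |
| Proportional, mean +22%, SD 25% | at least 30% worse, SAP scale | 36.4% | 34.3% |
| | rise of at least 30% of Baseline | 15.5% | 20.8% |

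With an additive rise, the SAP scale opens a gap of about 8 to 9 percentage points that is almost absent on the Baseline scale. With a mean change of 0, the median is 0% in both arms and the LX9211 curve is simply wider. With a proportional rise, the SAP scale is nearly neutral, and the Baseline scale shows a gap in the other direction. A display in points does the same, because 30% of an assumed Baseline of 6.5 is a fixed 1.95 points.

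**Step 3: undefined values.** Share of patients with a Week 6 mean of 0, for means of 4 and 5:

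- Week 6 SD 2: 2.5% on LX9211 and 0.7% on placebo. Per 75 completers this is 0.025 x 75 = 1.9 and 0.007 x 75 = 0.5 patients.
- Week 6 SD 1.5: 0.4% and 0.0%, or 0.004 x 75 = 0.3 and 0 patients.

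A second model builds Week 6 from a Baseline of about 6.5 plus a change with SD 2. It gives 2.3% and 0.7% when placebo improves by 1 point, and 6.1% and 2.3% when placebo improves by 2 points. All these figures come from a normal distribution cut off at 0.

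**Step 4: what else covers Week 6 to Week 11.** SAP 7.6.5.2 gives the clinic-visit Question 5 change from Baseline in points, and the full questionnaire is completed at Week 11. SAP 7.6.5.3 and 7.6.5.4 give weekly responder rates against Baseline, with weekly windows defined to Week 11 in Table 1.1. SAP 7.6.2.6 gives time to loss of efficacy, which counts only termination of follow-up for lack of efficacy. None of them shows each patient's diary change from Week 6.

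**The case against.** The strongest reply is that no scale is neutral. The Week 6 denominator distorts an additive rebound, and the Baseline denominator or a points scale distorts a proportional one. The documents do not say which pattern to expect. That stands: the case for change is not that Baseline is the correct denominator. It is that points and percent of Baseline use a scale that treatment has not altered, and give a value to every patient with both weekly scores.

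Second, the protocol names the endpoint as a percent change between these two weeks, and dividing by the earlier value is its ordinary reading. That also stands, and is a reason to keep the planned plot available.

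Third, a reader might infer that the plot must show LX9211 shifted toward worsening even without any rebound. It need not. Placebo patients go from placebo to placebo, and with a mean change of 0 the curve only widens. If pain returns because an effective drug is withdrawn, the arms truly differ: full return to an assumed 6.5 from 5.5 and 4.5 is 1 against 2 points (ratio 2.0), plotted as 18% against 44% (ratio 2.4). Most of that gap is real.

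Fourth, a reader might infer that this is almost the only view of the withdrawal period. SAP 7.6.5.2 to 7.6.5.4 contradict that. Nor do very large percentages spoil the whole plot: in a cumulative distribution they only sit at the far right.

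**Conclusion.** The point holds as a minor one. The direction is arithmetic: if LX9211 lowers Week 6 pain, an equal rise in points plots larger on LX9211, by a factor of 1.2 to 1.5 for Week 6 means 1 point apart within the range shown. That a Week 6 mean of 0 has no value and no rule follows directly from the formula and the scale. With no treatment effect at Week 6 there is no between-arm distortion of this kind.

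The sizes are conditional. The gap of roughly 8 to 9 percentage points needs an additive rebound with a mean of 1 point in both arms, and under a proportional rebound it shrinks to about 2 points. The loss of zero scorers is a couple of patients per arm at most under the main assumptions, though it could be larger if Week 6 scores spread further toward 0.

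The documents do not support reading this as a threat to the trial's conclusions. SAP 7.6 leaves the other endpoints unadjusted, SAP 7.6.5.6 plans no test, and other Week 11 summaries against Baseline exist. What is missing is a display of the within-patient diary change from Week 6 on a scale that does not depend on the Week 6 result.

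**What to change.** In SAP 7.6.5.6, plot the cumulative distribution of the Week 6 to Week 11 change in points, or of 100 x (Week 11 - Week 6)/Baseline ADPS. Use it as the main display or place it beside the percent-of-Week-6 plot. Where the latter is kept, state how a Week 6 score of 0 is handled and report the number of such patients by arm. Record the change in SAP Section 8, and align SAP 3.3 if the main display changes.

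Plotting the Week 11 percent change from Baseline next to the Week 6 curve of SAP 7.6.5.5 is not a substitute. It shows two separate distributions, from which a patient's own change cannot be read.

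The cost is one extra figure, or a minor change to a descriptive endpoint, using data already derived. As the working shows, the added scale has its own bias under a proportional rebound, so showing both displays is the safer choice.

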7.6.6 PK Analysis

C_{trough} values will be summarized at Weeks 2, 4, 6, and 11 using descriptive statistics by treatment group.

For the PK substudy, if quantifiable plasma concentrations are available, PK parameters will be derived using non-compartmental techniques, and their summarization will be based on descriptive and graphical methods and summarized for each dose level.

Plasma concentrations and time deviation data will be presented in the data listings by treatment, patient, and nominal time point. Plasma concentration data will be summarized descriptively by dose and nominal time point. Individual and mean plasma concentration versus nominal time profiles will be displayed graphically. All PK data will be presented in the data listings.

After the first 10 PK substudy patients complete the study, a blinded PK analysis may be done to confirm exposure following oral tablet administration.

As part of the PK substudy, additional samples will be collected for possible biomarker analyses. The actual and change from Baseline in biomarker/target engagement and chemokine/cytokine levels will be summarized descriptively at Weeks 2, 4, 6, and 11, by treatment group. Analyses will be performed on the mITT population with a Baseline and at least 1 valid post-Baseline data point.

7.7 Safety

7.7.1 Extent of Exposure

Duration of exposure to study drug in the double-blind Treatment Period will be defined as the total number of days of administration of the study drug:

(Date of last dose of double-blind study drug taken – date of first dose of double-blind study drug taken) + 1

Duration of exposure to study drug (days) in the double-blind Treatment Period will be summarized using descriptive statistics for each treatment group and overall for the Safety population.

The number and percentage of patients randomized and exposed to the study drug will also be presented by double-blinded treatment duration categories for each treatment group and overall for the Safety population.

- < 7 days
- ≥ 7 and < 14 days
- ≥ 14 and < 21 days
- ≥ 21 and < 28 days
- ≥ 28 and < 35 days
- ≥ 35 and < 42 days
- ≥ 42 days

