7.5 Dose Adjustment

Dose adjustments of any study drug are not permitted or applicable during the study. For safety reasons, should an unacceptable risk related to study drug arise, patients may be discontinued from the study. In the case of tolerability issues, the investigator can consider a temporary dose interruption of no less than 3 days, but no more than 5 days. If adverse event continues once study drug has been reinitiated then patient's continued participation needs to be assessed.

8. Study Procedures

A schedule of study assessments with detailed time points is provided in Appendix A.

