8.1.3 Safety Assessments

In addition to the clinical laboratory assessments described in Section 8.1.1, monitoring of AEs is also considered a safety assessment and is described in detail in Section 9. Clinically significant changes compared with baseline findings for these variables may be reported as AEs on the eCRF. Clinically significant changes compared with baseline values, which are determined to be adverse events should be followed until the event has resolved, the condition has stabilized, etiology of the event is determined to be not related to study drug, or the patient is lost to follow-up. In case a patient reports an AE, study drug may be held for up to 3 days to assess resolution, rather than discontinuing patient permanently from study participation. If the AE improves or resolves, study drug may be resumed. Prior to discontinuing a patient permanently from study participation, the Investigator should discuss with the Medical Monitor.

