10.4.1.1 Extent of study drug exposure

The extent of study treatment exposure will be assessed by the duration of treatment exposure during the study. The duration of treatment exposure will be the total number of days of administration of the study drug. The duration of study drug exposure will be calculated as: (Date of the last study drug taken – Date of the first study drug taken) + 1.

Descriptive statistics of duration of treatment exposure (number, mean, SD, minimum, median, and maximum) will be presented by treatment group. The number (%) of patients randomized and exposed to the study drug will be presented by visit/week for each treatment group.

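### Exposure is defined as days of administration but computed as a calendar span, so an interruption followed by resumed dosing counts as days on drug

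*SAP*

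**What the plan says.** SAP 7.7.1 states that duration of exposure in the double-blind period "will be defined as the total number of days of administration of the study drug". After a colon it gives the calculation: from "Date of last dose of double-blind study drug taken" subtract the date of the first such dose, then add 1. The result is summarised by arm and sorted into weekly categories, of which the top two are 35 to under 42 days and 42 days or more.

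Protocol 10.4.1.1 pairs the same definition with the same span formula: "The duration of treatment exposure will be the total number of days of administration of the study drug". Neither section subtracts days without dosing.

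Two Protocol sections allow dosing to stop and restart. Section 7.5 lets the investigator consider "a temporary dose interruption of no less than 3 days, but no more than 5 days" for tolerability. Section 8.1.3 says that after a reported adverse event "study drug may be held for up to 3 days to assess resolution", with dosing resumed if the event improves or resolves.

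SAP 7.7.2 reports the number and percentage of patients with an interruption due to an adverse event, but not the days involved. SAP 5.3.1 excludes from the per-protocol population patients with less than 5 weeks of double-blind treatment, checked from exposure data. It does not say which exposure measure is used.

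**The concern.** A count of dosing days and a calendar span are different quantities. When a patient stops for some days and restarts, the formula counts the gap in full and the definition excludes it. The programmed table would then carry a label that its numbers do not meet, and some interrupted patients would appear in the full-duration category.

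The summary of changes for Amendment 4 gives context, although the point does not depend on it. That amendment added the 3- to 5-day interruption and removed from the exposure definition a qualifier that had told the reader to disregard intermittent discontinuations. The qualifier had made the words fit the span formula, which stayed.

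At stake is the accuracy of a descriptive safety table and, possibly, membership of the per-protocol population.

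**Working it through.** The documents state no numerical exposure result, so there is no figure to reproduce. The check is date arithmetic.

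Inputs:
- Double-blind period of 6 weeks, or 42 days (SAP 2.2).
- Week 6 visit at target Day 43 (SAP Table 1.2) with a window of ±3 days (Protocol Appendix A), so Days 40 to 46.
- Gap g of 3, 4 or 5 days (Protocol 7.5). A 3-day gap is also the maximum under Protocol 8.1.3.
- First dose on Day 1.

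Formulas:
- Plan's formula: span = last dose day − 1 + 1 = last dose day.
- Plan's definition: days of administration = span − g.
- Check: with g = 0 and a last dose on Day 42, both give 42.

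Results for one gap followed by resumed dosing:

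| Last dose day | Formula | Days of administration (g = 3, 4, 5) | Does the category change? |
|---|---|---|---|
| 40 | 40 | 37, 36, 35 | No; both are 35 to under 42 |
| 42 | 42 | 39, 38, 37 | Yes, for every gap |
| 43 | 43 | 40, 39, 38 | Yes, for every gap |
| 46 | 46 | 43, 42, 41 | Only for the 5-day gap |

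For a last dose on Day 42, the overstatement is 3/42 = 7.1% to 5/42 = 11.9% of the reported span, or 3/39 = 7.7% to 5/37 = 13.5% of the days actually dosed.

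Effect on an arm mean: the documents give no interruption rate. Assuming that 5% to 15% of an arm has one 5-day gap with resumption, the mean is raised by 0.05 × 5 = 0.25 to 0.15 × 5 = 0.75 days, which is 0.6% to 1.8% of 42.

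Does another output correct this?
- The count of patients with adverse-event interruptions (SAP 7.7.2) gives no days and omits other reasons.
- Compliance (SAP 7.5) is tablets dispensed minus returned, over days in the period. A 5-day gap in 42 days gives 37/42 = 88.1%, inside the 80% to 100% compliant band. If the four Day 1 tablets count as dispensed while one tablet per day is expected, it gives (37 + 3)/42 = 95.2%, and a 3-day gap gives (39 + 3)/42 = 100%.
- Per-protocol check: if it uses the 7.7.1 formula, which is an assumption, a 35-day span with a 3- to 5-day gap passes on 32 to 30 dosed days. Other criteria in SAP 5.3 and 5.3.1, such as completing treatment through the six-week assessment and 80% compliance, may still exclude that patient.

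**The case against.** The strongest reply is that the formula follows a colon, is explicit and reproducible, and is the same in both documents. On that view it is the operative rule, and only the label is loose. This stands in part: the documents do not show which half is the mistake, and relabelling would resolve the mismatch as well as a new formula would.

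A second reply is pharmacological. Protocol 3.3 gives a mean half-life of 143 to 197 hours. Under simple first-order decline, the fraction remaining is 0.5^(t/half-life): about 71% to 78% after 72 hours and 56% to 66% after 120 hours. An interrupted patient is still exposed, so the span may be the more useful description. That is a good reason to report the span under its own name. It does not make the span a count of days of administration.

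A third reply is that little depends on the table. This stands. Protocol 10.4.5 rules out formal tests on safety data, and the SAP plans no exposure-adjusted event rates. Interruptions are also partly visible through the adverse-event interruption count, compliance and trough concentrations, although none of these corrects the exposure days.

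A reader might also infer that exposure is inflated most in the high-dose arm. The documents give no interruption rates by arm, and Protocol 3.4.1 expects both dose levels to be well tolerated, so that inference is conjecture.

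**Conclusion.** The definition and the formula contradict each other in both documents, and the formula gives a wrong result against the plan's own definition whenever dosing resumes after a gap. For a last dose on Day 42 with one gap of 3 to 5 days, the table shows 42 days instead of 39 to 37 and places the patient one category too high.

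The scope is limited. It would be tempting to say that every interrupted patient is overstated, but one who never restarts has no gap inside the span. Nor does every resumed patient move into the full-duration category, because that depends on the day of the last dose. The shift of 0.25 to 0.75 days in an arm mean rests entirely on the assumed 5% to 15% rate of one 5-day gap. The primary analysis is on the mITT population and is untouched. Only the supportive per-protocol analysis could be affected, and only if its 5-week check uses this formula. This is a minor point with a clear correction.

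**What to change.** In SAP 7.7.1 and Protocol 10.4.1.1:

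- Compute days of administration as (last dose date − first dose date + 1) minus recorded interruption days, and report the calendar span separately as treatment duration.
- If interruption dates are not captured, keep the formula and relabel the quantity as treatment duration including interruptions.
- State which measure drives the duration categories in SAP 7.7.1 and the 5-week check in SAP 5.3.1.
- Say how isolated missed doses are treated. Protocol 7.4 has them skipped, so subtracting only recorded interruptions would still count those days.

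The text change is small. The uncertain cost is data: the eCRF listed in SAP Section 1 is version 3 of 30 September 2020, before Amendment 4 of 09 September 2021, and the documents do not show that interruption start and stop dates are collected. That should be checked first, because it decides between the first two options.

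Separately, Protocol 7.5 (3 to 5 days) and Protocol 8.1.3 (up to 3 days) give different interruption lengths, which the sponsor must reconcile.
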